Based on results from comparable studies listed in Table 1 (onlay mesh versus suture) we estimate an IH rate of 30 % in group A and 10% in group B. We add on 20% loss to follow up at 12 months follow up due to the nature and known mortality rate in the emergency patient population amounting to about 70% of the laparotomies performed at SIH in 2023. With an alpha = 0.05 and power of 80% the number of patients needed in the study groups are 62 + 12 in each group, in total about 150 patients. If the loss to follow up turns out to be higher than 20%, the number of included patients will be increased accordingly.

8) Time frame

We plan to start the study in the autumn of 2024 after study approval and after training the involved surgeons and OR nurses in both the small stitch suture technique and the mesh application technique. We estimate inclusion to be complete at the end of 2026 and follow up at the end of 2027. During the following 6 months data will be analysed and the study results submitted for publication at the end of 2028.

9) Inclusion criteria

Surgery predominantly done by midline laparotomy
Age \geq 18 years
Written consent by patient/family
Midline laparotomy with delayed closure
No exclusion criteria

10) Exclusion criteria

Age $<$ 18 years
Pregnancy
Previous abdominal midline hernia mesh repair
Abdominal compartment syndrome
Linea alba closure not possible
Hernia in the midline with transverse diameter $>$ 2 cm
Life expectancy $<$ 6 months

11) Description of consent

Patients will be asked to participate in the study at the outpatient clinic or during their stay at the ward before surgery. Written consent is mandatory to be included in the study. The participants can at any time withdraw their consent. The patient data will from then on not be used in future analysis. If the anonymous data at the time is already included in the analysis, the data will not be deleted.

Elective surgery

The patients who are included in an elective setting will in most cases be identified at the outpatient clinic by a surgeon. This is not necessarily the same surgeon who will perform the surgery on the operating day. The patient will give consent to a resident, a junior doctor or a nurse either at the outpatient clinic when the medical record is taken or when the patient arrives at the ward before surgery. By not involving the

operating surgeon in this matter, the pressure of participating in the study will be reduced.

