In some cases, the planned procedure of laparoscopy will be converted to a midline laparotomy perioperatively. If there is a high risk of conversion preoperatively, the patient will be offered to participate in the study given that the surgery is converted to a laparotomy.

Emergency surgery

The risk of developing IH after an emergency surgery is increased (OR 4.7 CI 3.9-5.5) (30). The two studies published on onlay prophylactic synthetic mesh in emergency laparotomies show a reduction in IH in the mesh group (4% and 6%) compared to the group closed with suture alone (27,4% and 33%) (26,27). One study also shows a reduction in burst abdomen within the first 30 postoperative days (31). The current guidelines of European Hernia Society (EHS) and American Hernia Society (AHS) (32) make no recommendation regarding prophylactic mesh reinforcement in emergency laparotomy as “the data on mesh augmentation are heterogeneous and limited”. The guidelines states “More research is needed to draw definitive conclusions on potential benefits of mesh augmentation in patients undergoing emergency midline laparotomy and to identify subgroups of patients who might benefit from prophylactic mesh placement».

In our opinion it is critical to include emergency laparotomies in this study as this is the patient group where surgeons are most reluctant to implement prophylactic mesh even though these patients are probably benefiting the most from reinforcement. Some of these patients will not be able to be included in the study due to the urgency of the operation or the state of the patient. However, patients with Glasgow Coma Scale score 15 that can confirm why they need surgery and what the treatment plan is, will generally be eligible for study inclusion if there is time before surgery. As in an elective setting, the patient will give his consent to the resident, the junior doctor or the nurse on call and not to the operating surgeon, to reduce the patients perceived pressure to consent to the study.

12) End of study

The study will end when the desired numbers of participants have been included (150).

The study will be terminated if:

- The estimated inclusion timespan doubles from 1,5 years to more than 3 years.
- More than 30% of patients are lost to follow up during the first 12 months of the inclusion period significantly impacting on the estimated timeframe of the study.

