Patients will be interviewed and examined 4-6 weeks and 12 months after surgery in the outpatient clinic. In cases where the patient cannot show up to a clinical examination, a telephone interview will be performed. Incisional hernia occurrence will be evaluated clinically and by CT examination after 12 months. A QoL (EQ-5D) score and VAS-score will be performed preoperatively in patients scheduled for elective surgery. This cannot be performed in emergent cases due to considerable bias implicated by acute illness and the need for surgery. QoL (EQ-5D) score will be calculated at the scheduled postoperative follow ups in all patients. Total length of sick leave will also be registered as well as average pain over the last 24-48 hours measured by VAS-score. Any sign of symptomatic SSO will be further explored by ultrasound or CT scan at 4-6 weeks follow up.

In the application for study approval by the regional ethics committee and the local data protection officer, we will apply for storage of data over time to perform longterm follow up as well (5 years follow up). In accordance, we will ask for written consent from the patients to contact them after one and five years postoperatively.

21) Data storage and statistics

Registration forms will be stored in coded lockers in the department. Extracted data from electronical medical charts (DIPS extracted data) will be entered with identification code into Excel and thereafter transferred for analyses into SPSS. We might use LEDIDI for data storage if this system becomes available during the study period. The identification code will be stored separately on a safe institutional server domain approved and provided by the hospital.

Descriptive data analyses will be performed.

Continuous data will be analysed by Mann-Whitney U test and multiple logistic regression.

Categorical data will be analysed by Chi-Square tests and multiple logistic regression.

Kaplan-Meier analyses for IH rate comparison will be conducted.

Interim analyses of group differences will be performed as Mann-Whitney U test or Chi-Square tests as appropriate.

22) Ethics

Study approval will be applied to the regional ethics committee and the local data protection officer.

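### Do the 1.5-year baseline and the 30% loss rule in Section 12 of the protocol need changing?

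*Protocol*

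**What the plan says.** Section 12 (End of study) lists the conditions that terminate the trial. Two matter here. The first is accrual time: "The estimated inclusion timespan doubles from 1,5 years to more than 3 years". The second is loss: "More than 30% of patients are lost to follow up during the first 12 months of the inclusion period significantly impacting on the estimated timeframe".

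Section 8 (Time frame) gives the calendar: "We plan to start the study in the autumn of 2024 after study approval and after training the involved surgeons and OR nurses", and "We estimate inclusion to be complete at the end of 2026 and follow up at the end of 2027".

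Section 7 (Sample size) sets the planning figure for loss: "We add on 20% loss to follow up at 12 months follow up due to the nature and known mortality rate". The mortality meant is that of emergency patients. It also says what happens if that figure is exceeded: "If the loss to follow up turns out to be higher than 20%, the number of included patients will be increased accordingly".

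Section 20 (Evaluation/Follow up) fixes the contacts: "Patients will be interviewed and examined 4-6 weeks and 12 months after surgery in the outpatient clinic". Patients who cannot attend are interviewed by telephone.

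**The concern.** Both sentences can end the trial, so their stated basis deserves a check.

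On accrual time, the two sections give different planned inclusion periods. Section 12 suggests that accrual could fall to half of plan before the limit is reached. On Section 8's dates a much smaller shortfall gets there.

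On loss, Section 7 counts it at each patient's 12-month follow-up, while Section 12 counts it over the first 12 months of the inclusion period. With even accrual, patients at that moment have been followed for 6 months on average, and the 12-month visits have not fallen due. The share lost by then cannot, in expectation, exceed the eventual 12-month loss and will usually be lower. With only two scheduled contacts, a patient who drops out silently after the first visit is not noticed until the second. The rule could therefore stay quiet although 12-month loss will end above 30%.

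**Working it through.** **Accrual time**

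Inputs: 18 and 36 months (Section 12); autumn 2024, taken as 1 September to 30 November (an assumption), to the end of December 2026 (Section 8); 150 patients (Sections 7 and 12).

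- Section 12 on its own base: 2 × 18 = 36 months, so its arithmetic is right.
- Section 8: a 1 September start gives 28 months and a 30 November start gives 25 months. Neither gives 18.
- Ratio of limit to plan: 36/28 = 1.29; 36/25 = 1.44.
- Accrual per month: 150/18 = 8.33; 150/28 = 5.36; 150/25 = 6.00; at the limit 150/36 = 4.17.
- Shortfall that reaches the limit: 1 − 4.17/8.33 = 50% on Section 12's base; 1 − 4.17/5.36 = 22% to 1 − 4.17/6.00 = 31% on Section 8's dates.

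The baseline does not enter the condition that is applied. Inclusion has either run for more than 3 years or it has not.

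**Loss rule, read literally**

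Let F(u) be the proportion lost by u months after surgery. With even accrual (assumed), the proportion seen as lost at month 12 of inclusion is the mean of F(u) for u uniform on 0 to 12. For a true 12-month loss of 30%:

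| Timing of loss (assumed) | Calculation | Reading at month 12 | True loss at which 30% is read |
|---|---|---|---|
| All in month 1 | 0.30 × (1 − 0.5/12) = 0.30 × 0.9583 | 28.8% | 0.30/0.9583 = 31% |
| Half in month 1, half evenly over 12 months | 0.30 × (0.5 × 0.9583 + 0.5 × 0.5) = 0.30 × 0.7292 | 21.9% | 0.30/0.7292 = 41% |
| Constant hazard, λ = −ln 0.70 = 0.357 per year | 1 − 0.30/0.357 | 15.9% | 53% (solved numerically) |

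The shortfall is about 1 to 14 points. Loss that is seen only at the 12-month visit would not be read at all.

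**What follows if the rule stays silent**

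Section 7 then raises the number of patients. Taking that to mean keeping 62 evaluable per group:

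- Loss 30%: 62/0.70 = 88.6, so 89 per group and 178 in total. At Section 8's pace, 178/6.00 = 29.7 to 178/5.36 = 33.2 months, inside 3 years.
- Loss 53%: 62/0.467 = 132.8, so 133 per group and 266 in total. This takes 266/6.00 = 44.3 to 266/5.36 = 49.6 months, beyond 3 years, so the accrual limit would stop the trial.

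The information for that decision arrives in time. By the planned end of inclusion, patients from the first 25 − 12 = 13 to 28 − 12 = 16 months have a 12-month visit due: 13 × 6.00 = 78 to 16 × 5.36 = 86 of the 150.

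**What the alternatives would do**

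- A Kaplan-Meier estimate of 12-month loss at month 12 of inclusion (12 × 5.36 = 64 to 12 × 6.00 = 72 patients, constant hazard, simulated): with a true loss of 30%, the 95% range is about 12% to 58%. With a true loss at the planned 20%, the estimate exceeds 30% in about 12% of trials. The literal reading in that case averages 10.4%.
- The same estimate at month 18: range about 19% to 42% at a true 30%, and 3–4% of trials above 30% at a true 20%. By then 18/28 = 64% to 18/25 = 72% of the planned inclusion period has passed.
- Only patients whose visit is due, at month 18: 6 × 5.36 = 32 to 6 × 6.00 = 36 patients. The 95% half-width is 1.96 × √(0.3 × 0.7/n), which is 15.9 points for n = 32 and 15.0 for n = 36.

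**The case for a change.** The strongest case for a change is that these are termination criteria in the protocol itself, that one contradicts another section outright, and that correcting words costs almost nothing. The accrual sentence states its limit both as a ratio and as a number of years. On Section 8's dates a true doubling would be 50 to 56 months, so the two versions disagree. For loss, a rule that guards a planning figure ought to measure the same quantity, and under a constant hazard this one reads 30% only when true loss is 53%.

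Part of this stands. The two inclusion periods do not agree. The loss sentence leaves open whether the calendar window or each patient's own first 12 months is meant, and on the second reading the under-reading disappears.

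The rest does not carry. A sentence that names 3 years will be applied at 3 years, and the protocol sets no accrual-rate criterion that the wrong baseline could distort. The loss rule does not claim to estimate Section 7's 20%. It also requires the loss to be damaging the timetable, which marks it as an early feasibility check. The 53% depends on a hazard shape that the protocol does not give. Section 7 links its 20% to mortality in emergency patients, and deaths can become known without a scheduled visit. To the extent that loss comes soon after surgery, the gap is nearer 1 point than 14.

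**Conclusion.** No change to the plan follows. The 1.5-year figure is a clerical slip: it does not match Section 8's 25 to 28 months, but the 3-year limit, the sample size, the error rate and the estimate are the same with or without it.

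The loss rule is loosely worded, and read literally it under-reads 12-month loss by about 1 to 14 points at a true 30%, or more if drop-out is noticed only at the 12-month visit. The consequence is limited, because Section 7 answers excess loss by enlarging the trial and the 3-year limit caps that enlargement. At 30% loss the enlarged trial of 178 would still finish in about 30 to 33 months. A sharper measure is a trade-off without a clear gain: at month 12 it would put about 12% of on-plan trials over the 30% threshold, and a steadier version comes when about two thirds of inclusion is over.

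These figures assume even accrual at Section 8's pace, an autumn start between September and November 2024, and loss timings that are illustrations and not protocol data.
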